7.3.3.5. Tumor Size Change Over Time

Tumor size is defined as the sum of diameters of target lesions. The best percentage change from baseline, defined as the largest decrease in tumor size for each participant, will be summarized descriptively. In addition, the best percentage change may be presented by a waterfall plot. The analysis will be performed in all participants in the FAS with baseline tumor size available.

Per RECIST v1.1, target lesions considered "too small to measure" will be assigned a default value of 5 mm for the purposes of this analysis. Likewise, target lesions identified as "not present" at postbaseline assessments will be assigned 0 mm for this analysis. In the event a target lesion is unaccounted for in a particular postbaseline timepoint (ie, assessment missing or NE), then the overall sum of diameters for target lesions will not be evaluable for that timepoint.

8. SAFETY AND TOLERABILITY

Appendix A provides a list of planned tables, figures, and listings.

8.1. General Considerations

The clinical safety data (eg, vital signs, ECGs, routine laboratory tests, physical examinations, and AEs) will be summarized using descriptive statistics (eg, mean, frequency) by disease-specific cohort in safety evaluable population. Overall summaries combining all 4 disease-specific cohorts will be presented. If sufficient HIV-positive participants are enrolled into the study, safety data for those participants will be presented.

8.2. Adverse Events

8.2.1. Adverse Event Definitions

A TEAE is any AE either reported for the first time or worsening of a pre-existing event after first dose of study drug. Analysis of AEs will be limited to TEAEs, but data listings will include all AEs regardless of their timing to study drug administration. Adverse events will be tabulated by MedDRA SOC and PT. Severity of AEs will be based on the NCI CTCAE v5.0 using Grades 1 through 5 (NCI 2017). The CTCAE reporting guidelines and grading details are available on the Cancer Therapy Evaluation Program website.

The subset of AEs considered by the investigator to have a relationship to the study drug will be considered to be treatment-related AEs. If the investigator does not specify the relationship of the AEs to any component of study drug, the AE will be considered treatment-related. The incidence of AEs and treatment-related AEs will be tabulated.

An overall summary of AEs will include number (%) of participants reporting any TEAEs, any serious TEAEs, any Grade 3 or higher TEAEs, any treatment-related TEAEs, any fatal TEAEs, and any TEAEs leading to study drug interruption, dose reduction, or discontinuation and study withdrawal.

Number (%) of participants reporting any TEAEs, any serious TEAEs, any Grade 3 or higher TEAEs, any treatment-related TEAEs, any fatal TEAEs, and any TEAEs leading to treatment interruption, dose reduction, or discontinuation will be tabulated by MedDRA SOC and PT. Any missing onset date, causality, or severity must be queried for resolution. Unresolved missing causality and severity will be handled according to the following rules:

- An unresolved missing causality will be considered treatment-related.
- An unresolved missing severity will be identified as an unknown severity.

For purposes of analysis, all AEs will be considered TEAEs unless the AE can unequivocally be defined as not treatment-emergent.

Infusion-related reactions as well as irAEs (ie, AESIs) may be summarized separately.

8.2.2. Adverse Events of Special Interest

Immune-related AEs as well as infusion reactions will be considered AESIs in this study. Predefined PTs will be grouped into AESI categories and used to identify irAEs or infusion reactions without consideration of investigator's assessment of causality. Diagnosis of infusion

reactions occurring anytime during the treatment period, symptoms of infusion reactions that occur within 1 day of infusion, and resolve within 2 days from onset, will be considered infusion reactions. Adverse events of special interest identified by the investigator in the AE dataset will also be listed.

Immune-related AEs and infusion reactions will be summarized in separate tables. They will also be combined in an AESI overall summary table. An overall summary of AESIs will include the number (%) of participants reporting any AESIs, any ≥ Grade 3 AESIs, any treatment-related AESIs, any fatal AESIs, and any AESIs leading to infusion interruption, delay in planned treatment, or study drug discontinuation.

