3 or 4	Grade 3: Prolonged (ie, not rapidly responsive to symptomatic medication and/or brief interruption of infusion); recurrence of symptoms following initial improvement; hospitalization indicated for other clinical sequelae (eg, renal impairment, pulmonary infiltrates). Grade 4: Life-threatening; pressor or ventilatory support indicated.	Stop infusion and initiate appropriate medical therapy (eg, IV fluids, antihistamines NSAIDs, antipyretic, narcotics, oxygen, pressors, epinephrine, corticosteroids, per institutional preferences). Monitor vital signs frequently until medically stable. Hospitalization may be indicated.	Discontinue study drug.

Table 9: Guidelines for Management of Suspected Infusion Reaction

^a Per NCI CTCAE v5.0, appropriate resuscitation equipment should be available at the bedside and a physician readily available during the period of study drug administration.

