8.4. Pharmacokinetic Assessments

Assessment of PK is an important objective of this study, representing the first clinical experience with administration of INCMGA00012 as a 30-minute infusion. Blood samples for PK analysis will be obtained at the visits and timepoints indicated in Table 4.

After the preinfusion PK sample is drawn, participants will begin the study drug infusion. Adjustments to the timing of blood sampling may be made based on emerging PK data. The exact dates and times of the PK blood collection will be recorded in the eCRF. Instructions for sample preparation and shipping will be provided in the Laboratory Manual.

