1.5 Others		
1.5	Summary of General Medical History	FAS
2 Efficacy		
2.1.1	Summary of Best Overall Response According to RECIST v1.1	FAS
2.2.1	Summary of Duration of Response According to RECIST v1.1	FAS
2.2.2	Summary of Progression-Free Survival According to RECIST v1.1	FAS
2.2.3	Summary of Overall Survival	FAS
2.2.4	Summary of Largest Percentage Reduction in Sum of Diameters of Target Lesions	FAS
Safety	· · · · · · · · · · · · · · · · · · ·	
3.1 Dose Expo	sure	
3.1.1	Summary of Exposure to INCMGA00012	Safety Evaluable
3.1.2	Summary of INCMGA00012 Dose Delay/Interruption	Safety Evaluable

Table No.	Title	Population
3.2 Adverse l	Events	
3.2.1.1	Overall Summary of Treatment-Emergent Adverse Events	Safety Evaluable
3.2.1.2	Overall Summary of Treatment-Emergent Adverse Events of Special Interest	Safety Evaluable
3.2.1.3	Overall Summary of Treatment-Emergent Infusion Reaction	Safety Evaluable
3.2.1.4	Overall Summary of Treatment-Emergent Immune Related Adverse Events	Safety Evaluable
3.2.2.1	Summary of Treatment-Emergent Adverse Events by MedDRA System Organ Class and Preferred Term	Safety Evaluable
3.2.2.2	Summary of Treatment-Emergent Infusion Reaction by Group Term and Preferred Term	Safety Evaluable
3.2.2.3	Summary of Treatment-Emergent Immune Related Adverse Events by Group Term and Preferred Term	Safety Evaluable
3.2.3.1	Summary of Treatment-Emergent Adverse Events by MedDRA Preferred Term in Decreasing Order of Frequency	Safety Evaluable
3.2.4.1	Summary of Treatment-Emergent Adverse Events by MedDRA System Organ Class, Preferred Term, and Maximum Severity	Safety Evaluable
3.2.4.2	Summary of Treatment-Emergent Infusion Reaction by Group Term, Preferred Term, and Maximum Severity	Safety Evaluable
3.2.4.3	Summary of Treatment-Emergent Immune Related Adverse Events by Group Term, Preferred Term, and Maximum Severity	Safety Evaluable
3.2.6.1	Summary of Grade 3 or Higher Treatment-Emergent Adverse Events by MedDRA System Organ Class and Preferred Term	Safety Evaluable
3.2.6.2	Summary of Grade 3 or Higher Treatment-Emergent Infusion Reaction by Group Term and Preferred Term	Safety Evaluable
3.2.6.3	Summary of Grade 3 or Higher Treatment-Emergent Immune Related Adverse Events by Group Term and Preferred Term	Safety Evaluable
3.2.7	Summary of Grade 3 or Higher Treatment-Emergent Adverse Events by MedDRA Preferred Term in Decreasing Order of Frequency	Safety Evaluable

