3.2.8	Summary of Serious Treatment-Emergent Adverse Events by MedDRA System Organ Class and Preferred Term	Safety Evaluable
3.2.9	Summary of Serious Treatment-Emergent Adverse Events by MedDRA Preferred Term in Decreasing Order of Frequency	Safety Evaluable
3.2.10	Summary of Treatment-Related Treatment-Emergent Adverse Events by MedDRA System Organ Class and Preferred Term	Safety Evaluable
3.2.11	Summary of Treatment-Related Treatment-Emergent Adverse Events by MedDRA Preferred Term in Decreasing Order of Frequency	Safety Evaluable
3.2.14	Summary of Treatment-Related Grade 3 or Higher Treatment-Emergent Adverse Events by MedDRA System Organ Class and Preferred Term	Safety Evaluable
3.2.15	Summary of Treatment-Related Serious Treatment-Emergent Adverse Events by MedDRA System Organ Class and Preferred Term	Safety Evaluable
3.2.16.1	Summary of Treatment-Emergent Adverse Events With a Fatal Outcome by MedDRA System Organ Class and Preferred Term	Safety Evaluable

3.2.16.2	Summary of Treatment-Emergent Infusion Reaction With a Fatal Outcome by	Safety
	Group Term and Preferred Term	Evaluable
3.2.16.3	Summary of Treatment-Emergent Immune Related Adverse Events With a	Safety
	Fatal Outcome by Group Term and Preferred Term	Evaluable

Table No.	Title	Population
3.2.19.1	Summary of Treatment-Emergent Adverse Events Leading to Infusion Interruption by MedDRA System Organ Class and Preferred Term	Safety Evaluable
3.2.19.2	Summary of Treatment-Emergent Infusion Reaction Leading to Infusion Interruption by Group Term and Preferred Term	Safety Evaluable
3.2.19.3	Summary of Treatment-Emergent Immune Related Adverse Events Leading to Infusion Interruption by Group Term and Preferred Term	Safety Evaluable
3.2.19.4	Summary of Treatment-Emergent Adverse Events Leading to Next Scheduled Dose Delay by MedDRA System Organ Class and Preferred Term	Safety Evaluable
3.2.19.5	Summary of Treatment-Emergent Infusion Reaction Leading to Next Scheduled Dose Delay by Group Term and Preferred Term	Safety Evaluable
3.2.19.6	Summary of Treatment-Emergent Immune Related Adverse Events Leading to Next Scheduled Dose Delay by Group Term and Preferred Term	Safety Evaluable
3.2.20.1	Summary of Treatment-Emergent Adverse Events Leading to Discontinuation of Study Drug by MedDRA System Organ Class and Preferred Term	Safety Evaluable
3.2.20.2	Summary of Treatment-Emergent Infusion Reaction Leading to Discontinuation of Study Drug by Group Term and Preferred Term	Safety Evaluable

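### Symptom-coded infusion reactions that outlast 2 days, stay unresolved or are fatal drop out of the SAP's infusion-reaction tables, which can therefore understate severe reactions

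*SAP*

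**What the plan says.** SAP 8.2.2 makes infusion reactions one of two groups of adverse events of special interest (AESIs), the other being immune-related events. Candidate events are found from a predefined list of preferred terms, "used to identify irAEs or infusion reactions without consideration of investigator's assessment of causality". There are then two ways in:

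- **Diagnosis.** The SAP counts diagnosed "reactions occurring anytime during the treatment period". On the natural reading no duration test applies.
- **Symptom.** For events recorded as signs or symptoms the rule is: "symptoms of infusion reactions that occur within 1 day of infusion, and resolve within 2 days from onset, will be considered infusion reactions".

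The resulting category feeds the overall AESI summary and a set of tables in SAP Appendix A. These include Table 3.2.6.2 ("Summary of Grade 3 or Higher Treatment-Emergent Infusion Reaction by Group Term and Preferred Term"), Table 3.2.16.2 (titled "Summary of Treatment-Emergent Infusion Reaction With a Fatal Outcome by" group term and preferred term) and Table 3.2.20.2 (reactions leading to discontinuation of study drug). The SAP adds one listing: "Adverse events of special interest identified by the investigator in the AE dataset will also be listed".

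On the Protocol side, Table 9 in Section 6.5.1 describes a Grade 3 reaction as "Prolonged (ie, not rapidly responsive to symptomatic medication and/or brief interruption of infusion"), as one that recurs after initial improvement, or as one needing hospitalization for sequelae. Protocol 8.3.1 and 9.3 prefer a diagnosis to its component symptoms, and have symptoms recorded separately when no clear diagnosis can be made.

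**The concern.** Onset within 1 day ties a symptom to the infusion. Resolution within 2 days does something different: it admits or rejects the event according to how it turned out. A severe reaction is plausibly slower to resolve than a mild one, so among symptom-coded events the filter tends to work against the cases that the severity, fatal and discontinuation tables exist to show. A low or zero entry there could come from the definition rather than from the drug.

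This also runs against the rest of the SAP's safety approach. Section 8.2.1 treats missing causality as related, and treats every adverse event as treatment-emergent unless it is clearly not. Infusion tolerability is of some interest here, since Protocol 8.4 describes the study as "representing the first clinical experience with administration of INCMGA00012 as a 30-minute infusion". That sentence is about pharmacokinetics, however, and is context only.

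**Working it through.** The documents state no infusion-reaction rate, so there is no figure to reproduce. The check applies the rule case by case.

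**Inputs**
- The two entry routes: SAP 8.2.2.
- Outcome categories: Protocol 9.3 lists fatal and unresolved as outcomes distinct from resolved.
- Missing-data rules for adverse events: SAP 8.2.1 covers onset date, causality and severity. It has no rule for a missing end date.
- Planned sizes: about 30 per cohort and about 120 overall (Protocol Section 1, Table 2).
- Assumption: the symptom's preferred term is on the predefined list, which the documents do not show.

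**Rule applied**

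| Recorded as | Course | In the infusion-reaction tables? |
|---|---|---|
| Diagnosis | Any duration, unresolved or fatal | Yes |
| Symptom, onset within 1 day | Resolved within 2 days, any grade including 3 or 4 | Yes |
| Symptom, onset within 1 day | Resolved after more than 2 days | No |
| Symptom, onset within 1 day | Not resolved | No |
| Symptom, onset within 1 day | Fatal | No |
| Symptom, onset within 1 day | End date missing | Not determined by the SAP |

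It follows that a symptom-coded event can never enter Table 3.2.16.2, because a fatal outcome is not a resolution. It can enter Tables 3.2.6.2 and 3.2.20.2 only if it resolved within 2 days.

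**Illustration (hypothetical).** Grade 3 hypotension begins 1 hour after infusion, resolves on day 4 and leads to discontinuation. Recorded as an infusion reaction, it counts in Tables 3.2.6.2 and 3.2.20.2. Recorded as hypotension, it counts in neither, and appears only in the general TEAE tables under hypotension.

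**Weight of one omitted participant**
- One cohort: 1/30 = 3.3 percentage points.
- All cohorts: 1/120 = 0.8 percentage points.

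These are the weight of one person, not an estimate of bias.

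**The case against.** The case for leaving the rule alone has real substance.

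- **Diagnosis coding is preferred.** A severe reaction that a site recognizes, reports to the medical monitor within 24 hours (Protocol 6.5.1) and manages under Table 9 should normally be recorded as a diagnosis, and would be counted. This stands, and it limits how often the gap matters. It does not close the gap: Protocol 9.3 provides for symptom records when no clear diagnosis can be made, and the SAP has a symptom route for them.
- **No event disappears.** Excluded events remain in the general Grade 3 or higher, serious, fatal and discontinuation tables. This also stands, but there they appear under their own terms and cannot correct the infusion-reaction counts. The listing of investigator-identified AESIs (Listing 2.7.9) is weak support, because Protocol 9.5 names only potentially immune-related events as AESIs. Investigators are not asked there to flag infusion reactions.
- **The filter has a purpose.** Terms are picked without regard to causality, so timing is what separates infusion symptoms from tumor symptoms and immune-related events. This stands, and it is a reason to keep the filter for lower-grade symptoms.

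A reader might infer that prolonged, unresolved and fatal reactions are all removed by definition. The documents do not support that, because diagnosis-coded reactions carry no duration test. The sentence in 8.2.2 is loosely built, and if the 2-day condition governed diagnoses too the exclusion would be general. The list structure and the word for any time make that reading the less likely one.

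A reader might also take Table 9's term for a prolonged reaction to mean more than 2 days. Table 9 defines it by slow response to treatment and gives no number of days.

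**Conclusion.** The point holds for symptom-coded events. Those starting within 1 day of infusion that last more than 2 days, do not resolve or are fatal are excluded from all infusion-reaction tables by a stated rule that selects on outcome. Tables 3.2.6.2, 3.2.16.2 and 3.2.20.2 can therefore understate severe reactions.

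The size cannot be estimated, since neither the reaction rate nor the share coded as symptoms is given. Where severe counts are small, one omission could turn a nonzero row into zero.

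Three stronger conclusions are not supported. Table 3.2.6.2 is not emptied, because Grade 3 or 4 symptoms that resolve within 2 days still count. A missing end date is undetermined, not excluded. Nor is a net downward bias in the overall infusion-reaction rate shown, because the causality-blind term search can also over-count.

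The conclusion rests on reading the 2-day condition as applying to symptoms only, and on the relevant symptom terms being on the predefined list. That severe reactions resolve more slowly is plausible, but the documents do not establish it.

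**What to change.** Amend SAP 8.2.2 as follows:

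1. For symptoms on the predefined term list that start within 1 day of infusion, drop the 2-day resolution condition if the event is Grade 3 or higher, serious or fatal, or led to infusion interruption or study drug discontinuation.
2. Keep the condition for other Grade 1 or 2 symptoms, including ongoing ones. Exempting every unresolved or undated low-grade symptom would admit unrelated events, such as ongoing mild dyspnea in the lung cancer cohort if that term is listed.
3. State how a missing end date is handled.
4. Show infusion-reaction counts with and without the duration filter.

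The cost is short SAP wording and some programming. No new data are needed and clinical management does not change. The downside is that, because terms are selected without regard to causality, some severe events unrelated to the infusion may be counted. The with-and-without display makes that visible.

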8.2.3. Adverse Event Summaries

An overall summary of AEs may include the following:

- Number (%) of participants reporting any TEAEs
- Number (%) of participants reporting any serious TEAEs
- Number (%) of participants reporting any Grade 3 or higher TEAEs
- Number (%) of participants reporting any TEAEs related to study drug
- Number (%) of participants reporting any serious TEAEs related to study drug
- Number (%) of participants reporting any Grade 3 or higher TEAEs related to INCMGA00012
- Number (%) of participants who temporarily interrupted study drug infusion because of TEAEs
- Number (%) of participants who delayed next scheduled dose because of TEAEs
- Number (%) of participants who permanently discontinued INCMGA00012 because of TEAEs
- Number (%) of participants who had a fatal TEAE
- Number (%) of participants who withdrew from study because of TEAEs The following summaries may be produced by MedDRA term:
- Summary of TEAEs by SOC and PT
- Summary of TEAEs by PT in decreasing order of frequency
- Summary of TEAEs by SOC, PT, and maximum severity
- Summary of Grade 3 or higher TEAEs by SOC and PT
- Summary of Grade 3 or higher TEAEs by PT in decreasing order of frequency
- Summary of serious TEAEs by SOC and PT
- Summary of serious TEAEs by PT in decreasing order of frequency
- Summary of treatment-related TEAEs by SOC and PT
- Summary of treatment-related TEAEs by PT in decreasing order of frequency
- Summary of treatment-related Grade 3 or higher TEAEs by SOC and PT

- Summary of treatment-related serious TEAEs by SOC and PT
- Summary of TEAEs with a fatal outcome by SOC and PT
- Summary of TEAEs leading to infusion interruption by SOC and PT
- Summary of TEAEs leading to infusion delay in next scheduled dose by SOC and PT
- Summary of leading to study drug discontinuation by SOC and PT
- Summary of infusion-related reactions by SOC and PT
- Signs/symptoms of infusion-related reactions
- Summary of nonserious TEAEs by PT in decreasing order of frequency The following summaries for AEs of special interest will be included:
- Overall summary of TEAEs of special interest
- Summary TEAEs of special interest by group term and PT
- Summary TEAEs of special interest by group term, PT, and maximum severity
- Summary of Grade 3 or higher TEAEs of special interest by group term and PT
- Summary of TEAEs of special interest with a fatal outcome by group term and PT
- Summary of TEAEs of special interest leading to infusion interruption by group term and PT
- Summary of TEAEs of special interest leading to infusion delay in next scheduled dose by group term and PT
- Summary of TEAEs of special interest leading to study drug discontinuation by group term and PT

8.3. Clinical Laboratory Tests

8.3.1. Laboratory Value Definitions

Laboratory values and change from baseline values will be summarized descriptively by visit. Baseline will be determined according to Section 4.1.4. If there are multiple values that meet the criteria for baseline, Table 5 will delineate which value will be defined as baseline.

Table 5: Baseline Laboratory Identification

Priority	Laboratory Visit	Proximity to Visit Window	Tiebreaker
1	Scheduled	In-window	Use smallest laboratory
2	Unscheduled	In-window	sequence number
3	Scheduled	Out-of-window	

Laboratory test values outside the normal range will be assessed for severity based on CTCAE grade or similar criteria where clinical intervention is required for CTCAE grading. The incidence of abnormal laboratory values will be listed.

8.3.2. Laboratory Value Summaries

All test results and associated normal ranges from laboratories will be reported in SI units. Any laboratory test results and associated normal ranges from local laboratories will be converted to SI units. For test results that will be summarized with available normal ranges, the number and percentage of participants with the laboratory values being low (but never high), normal, high (but never low), and both low and high will be calculated for each test. This shift summary may be produced for each test for safety evaluable population. The denominator for the percentage calculation will use the number of participants in the baseline category (ie, low, high, normal, missing) as the denominator for the percentage in each of the categories during the treatment period. For numeric laboratory values, baseline value, postbaseline value, change from baseline, and percentage change from baseline will be summarized by visit.

Separate summaries for abnormally high and abnormally low laboratory values will be provided when the laboratory parameter has both high and low grading criteria. The denominator for the percentage calculation will be the number of participants in the baseline category.

The following summaries will be produced for laboratory data (by laboratory parameter) reported on-treatment.

- Number and percentage of participants with worst postbaseline CTC grade (regardless of the baseline status). Each participant will be counted only for the worst grade observed postbaseline.
- Shift tables using CTCAE grades comparing baseline with the worst postbaseline value will be produced for hematology and biochemistry laboratory parameters with CTCAE grades.

- For laboratory parameters where CTCAE grades are not defined, shift tables to the worst postbaseline value will be produced using the low/normal/high classifications based on laboratory reference ranges.
- For laboratory parameters with any worsening postbaseline CTC grades than baseline, the worst postbaseline CTC grades will be summarized according to CTC severity grade levels. If baseline grade is missing, any postbaseline abnormality (Grade 1-4) is considered worsening from baseline.
- Number and percentage of participants meeting categorical liver function test criteria, including ALT, AST, and ALT or AST (> 3, 5, 8, 10, and 20 × ULN), total bilirubin (> 1 and 2 × ULN), ALP (> 1.5, 2, 3, 5, 8, and 10 × ULN), combined categories of ALT/AST and total bilirubin (eg, ALT or AST > 3 × ULN and total bilirubin > ULN) as well as laboratory Hy's Law criteria without medical adjudication (ALT or AST > 3 × ULN and total bilirubin > 2 × ULN and ALP < 2 × ULN at the same visit or within a specified number of days). The worst values observed postbaseline for each participant will be used for each of the categories. The summary will be presented by baseline liver metastases status.

